A screening visit will occur within 30 days of signing an informed consent form (ICF). During the screening phase, subjects will be evaluated for eligibility to participate in the study. Subjects who meet the protocol criteria may be admitted in the evening to the clinical study center, or visit the clinic if staying locally, on day -1. For Cycle 1, subjects may be admitted to the clinical study center during PK sampling periods or must agree to stay locally with frequent clinic visits as required and, optional admission to the center, if available. Prior to dosing on day 1 of Cycle 1, subject eligibility will be reconfirmed. On day 1, a single oral dose of 400 mg tazemetostat will be administered in the morning (eg, 7 – 9 am) followed by 2 days of multiple blood sampling (day 1 – 3). From day 3 – 14, subjects will receive an oral 400 mg dose of tazemetostat twice daily (12 hours apart, once in the morning [eg, 7 – 9 am] and once in the evening [eg, 7 – 9 pm]). In the evening of day 14, subjects may be admitted to the clinical study center. On day 15, a single oral dose of 400 mg tazemetostat will be administered in the morning (eg, 7 – 9 am) followed by 3 days of multiple blood sampling (day 15 – 18). From day 18 – 20, a single dose of oral 200 mg itraconazole will be administered daily in the morning (eg, 7 – 9 am) after a meal. In the evening of day 20, subjects may be admitted to the clinical study unit. From day 21 – 35, subjects will receive an oral 400 mg dose of tazemetostat twice daily, once in the morning (eg, 7 – 9 am) and once in the evening (eg, 7 – 9 pm), co-administered in the morning (eg, 7 – 9 am) after a meal with a single dose of oral 200 mg itraconazole followed by 1 day of multiple blood sampling (day 21 – 22). In the evening of day 35, subjects may be admitted to the clinical study center. On day 36, subjects will receive a single oral dose of 400 mg tazemetostat co-administered in the morning (eg, 7 – 9 am) after a meal with a single dose of oral 200 mg itraconazole followed by 3 days of multiple blood sampling (day 36 – 39). Itraconazole will also be administered on day 37 and 38 as a single oral 200 mg daily dose in the morning (eg, 7 – 9 am) after a meal. **Note:** Tazemetostat will not be administered on day 37 and 38. After the 72-hour PK sample collection, safety assessments will be conducted on day 39. Sparse PK samples will be collected pre-dose (0 hour) and 2 hours post-dose on day 25, 28, 31, and 34.

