A screening visit will occur within 30 days of signing an informed consent form (ICF). During the screening phase, subjects will be evaluated for eligibility to participate in the study. Subjects who meet the protocol criteria may be admitted in the evening to the clinical study center, or visit the clinic if staying locally, on day -1. For Cycle 1 subjects may be admitted to the clinical study center during PK sampling periods or must agree to stay locally with frequent clinic visits as required and optional admission to the center if available. Prior to dosing on day 1 of Cycle 1, subject eligibility will be reconfirmed. On day 1, a single oral dose of 800 mg tazemetostat will be administered in the morning (eg, 7 – 9 am) followed by 2 days of multiple blood sampling (day 1 – 3). From day 3 – 14, subjects will receive an oral 800 mg dose of tazemetostat twice daily (12 hours apart once in the morning [eg, 7 – 9 am] and once in the evening [eg, 7 – 9 pm]). In the evening of day 14, subjects may be admitted to the clinical study center. On day 15, a single oral dose of 800 mg tazemetostat will be administered in the morning (eg, 7 – 9 am) followed by 2 days of multiple blood sampling (day 15 – 17). From day 17 – 23, subjects will receive an oral 800 mg dose of tazemetostat twice daily, once in the morning (eg, 7 – 9 am) and once in the evening (eg, 7 – 9 pm), co-administered in the morning (eg, 7 – 9 am) one hour before a meal with a single dose of oral 600 mg rifampin. In the evening of day 23, subjects may be admitted to the clinical study center. On day 24, subjects will receive a single oral dose of 800 mg tazemetostat co-administered in the morning (eg, 7 – 9 am) one hour before a meal with a single dose of oral 600 mg rifampin followed by 2 days of multiple blood sampling (day 24 – 26). Rifampin will also be administered on day 25 as a single oral 600 mg dose in the morning (eg, 7 – 9 am) one hour before a meal. **Note:** Tazemetostat will not be administered on day 25. After the 48-hour PK sample collection, safety assessments will be conducted on day 26. Sparse PK samples will be collected pre-dose (0 hour) and 2 hours post-dose on day 19 and 21.

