7.4. Restrictions During Study Treatment

Subjects will abstain from ingesting Seville oranges, grapefruit or grapefruit juice, and foods/beverages that contain those, for 24 hours prior to the first dose of study treatment until the last dose of study treatment.

Subjects should avoid prolonged exposure to sunlight while receiving study treatment. In addition, subjects should take other measures to avoid ultraviolet exposure including tanning beds. Use sunscreen, sunglasses, and protective clothing whenever outside.

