ⁿ **Laboratory Assessments:** Lab assessments for Cycle 1 will be performed at screening, day 1, 3, 15, 18, 21, 22, 36, and day 39. For all subjects, laboratory assessments may be performed within 24 hours prior to the day on which they are required (ie, day -1, 2, 14, 17, 20, 21, 35, and 38) to ensure results are available for review prior to dosing of study drug(s) the following day. For Cycle 2+, laboratory assessments will be performed at the beginning of each cycle on day 1 and at the end of study. Refer to [Appendix 2](#) for a complete list of the clinical laboratory tests to be conducted. In addition, a complete peripheral blood smear morphology assessment (see Blood Smear Guidance in laboratory manual) will be performed manually or automated along with routine hematology testing at screening and during the study by the local laboratory. If the peripheral blood smear morphology results are abnormal and suggestive of MDS/AML or MPN, the subject will undergo a bone marrow aspirate/biopsy procedure. The bone marrow aspirate/biopsy sample will then be analyzed by cytogenetic testing at the local laboratory to closely monitor subjects for abnormalities known to be associated with MDS (eg, del 5q, chr 7, abn) and MPN (eg, JAK2 V617F). Additional local laboratory testing of genetic aberrations associated with MDS/AML or MPN can be conducted using targeted next generation sequencing (NGS) of known disease genes, as necessary. If local testing is unavailable or if results are inconclusive/indeterminate, the site will be required to ship samples for central laboratory testing. If the cytogenetic testing and, if conducted, DNA sequencing by NGS results are abnormal and associated with myeloid malignancies, tazemetostat will be discontinued. See [Section 12.3.7](#) for further details.

^o **Tazemetostat Administration (QD):** During Cycle 1, subjects will receive a single oral dose of 400 mg tazemetostat on day 1, 15, and day 36 in the morning (eg, 7 – 9 am).

^p **Tazemetostat Administration (multi-dose):** Subjects will receive an oral 400 mg dose of tazemetostat twice daily during Cycle 1 from day 3 – 14 and day 21 – day 35. During subsequent cycles (Cycle 2+), dosing will begin on day 1 whereby subjects will receive 800 mg tazemetostat twice daily. Tazemetostat is to be taken twice daily 12 hours apart, once in the morning (eg, 7 – 9 am) and once in the evening (eg, 7 – 9 pm).

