- ^m **AEs/SAEs:** AEs/SAEs and non-serious adverse events will be collected from the time the subject signs the consent form until the end of the safety reporting period (or until screen failure). The safety reporting period ends 30 days after the last dose of study drug, or initiation of an investigational agent or cytotoxic chemotherapy, whichever occurs first.
- ⁿ **Laboratory Assessments:** Lab assessments for Cycle 1 will be performed at screening, day 1, 3, 15, 17, 24, and 26. For all subjects, laboratory assessments may be performed within 24 hours prior to the day on which they are required (ie, day -1, 2, 14, 16, 23, and 25) to ensure results are available for review prior to dosing of study drug(s) the following day. For Cycle 2+, laboratory assessments will be performed at the beginning of each cycle on day 1 and at the end of study. Refer to [Appendix 2](#) for a complete list of the clinical laboratory tests to be conducted. In addition, a complete peripheral blood smear morphology assessment (see Blood Smear Guidance in laboratory manual) will be performed manually or automated along with routine hematology testing at screening and during the study by the local laboratory. If the peripheral blood smear morphology results are abnormal and suggestive of MDS/AML or MPN, the subject will undergo a bone marrow aspirate/biopsy procedure. The bone marrow aspirate/biopsy sample will then be analyzed by cytogenetic testing at the local laboratory to closely monitor subjects for abnormalities known to be associated with MDS (eg, del 5q, chr 7, abn) and MPN (eg, JAK2 V617F). Additional local laboratory testing of genetic aberrations associated with MDS/AML or MPN can be conducted using targeted next generation sequencing (NGS) of known disease genes, as necessary. If local testing is unavailable or if results are inconclusive/indeterminate, the site will be required to ship samples for central laboratory testing. If the cytogenetic testing and, if conducted, DNA sequencing by NGS results are abnormal and associated with myeloid malignancies, tazemetostat will be discontinued. See [Section 12.3.7](#) for further details.
- ^o **Tazemetostat Administration (QD):** During Cycle 1, subjects will receive a single oral dose of 800 mg tazemetostat on day 1, 15, and day 24 in the morning (eg, 7 – 9 am).

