9.3. Treatment Compliance

The subject will be requested to maintain a medication diary documenting each dose of tazemetostat as well as itraconazole or rifampin. The dosing diary will need to be returned to the site staff at each clinic visit.

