10.5. Study Drug Administration

Tazemetostat must be dispensed or administered only to subjects enrolled in the study and in accordance with the protocol. Standard institutional procedures for administering an oral agent will be followed. An adequate supply will be provided with instructions on home administration. Tazemetostat (400 mg for Part 1 and 800 mg for Part 2) doses must be taken at least 12 hours apart at approximately the same time each day, for example between 7 – 9 am for the morning dose and 7 – 9 pm for the evening dose. Administration of itraconazole, whether alone or concomitantly with tazemetostat, must be after a meal. Rifampin dosing, whether alone or co-administered with tazemetostat, must be one hour before a meal.

Part 1: Tazemetostat and Itraconazole Drug Interaction

Part 1 of the study will evaluate the drug-drug interaction between tazemetostat and itraconazole in an open-label, fixed sequential cross over design (Figure 2).

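### The meal state of the tazemetostat dose is fixed on the co-administration PK days (Day 36, Day 24) but not on the Day 15 reference day, so food could bias the primary ratio in both parts

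*Protocol*

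**What the plan says.** Section 10.5 of the protocol sets meal conditions through the partner drugs: "Administration of itraconazole, whether alone or concomitantly with tazemetostat, must be after a meal" and "Rifampin dosing, whether alone or co-administered with tazemetostat, must be one hour before a meal". Sections 7.1 and 10.5 carry these rules to the test-day tazemetostat doses, so Day 36 in Part 1 is after a meal and Day 24 in Part 2 is one hour before one.

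The Day 15 dose gets no such condition. Section 7.1 says for Part 1 "On day 15, a single oral dose of 400 mg tazemetostat will be administered in the morning" and for Part 2 "On day 15, a single oral dose of 800 mg tazemetostat will be administered in the morning", each followed only by a 7–9 am example. Footnote o of Table 3 ("subjects will receive a single oral dose of 400 mg tazemetostat on day 1, 15, and day 36 in the morning") and of Table 4 ("subjects will receive a single oral dose of 800 mg tazemetostat on day 1, 15, and day 24 in the morning") adds nothing on food, nor do the synopsis, the Section 10.5 narrative or SAP Section 3.1. Section 7.4 begins "Subjects will abstain from ingesting Seville oranges, grapefruit or grapefruit juice" and otherwise covers only sun exposure. Section 9.3 asks subjects to "maintain a medication diary documenting each dose of tazemetostat as well as itraconazole or rifampin", and Section 11.1 records dosing and sampling times. Neither mentions meals.

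Section 13.2 makes Day 15 the tazemetostat-alone period, set against Day 36 and Day 24. Section 5.2.2 describes the food effect as negligible, reports no difference between low-fat and high-fat meals, and gives decreases of 24% in Cmax and 18% in AUC after a high-fat meal.

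**The concern.** The comparison is within subject but in fixed sequence. Anything that differs systematically between Day 15 and the test day travels with treatment, and the pairing does not cancel it. A site following the text exactly could pair a fasted Day 15 with a fed Day 36, or a fed Day 15 with a pre-meal Day 24. The ratio would then estimate interaction times food effect.

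In each part the mismatch that can arise works against the expected result. Food lowers exposure, so a fed Day 36 over a fasted Day 15 pulls down a ratio that inhibition should raise. A pre-meal Day 24 over a fed Day 15 pushes up a ratio that induction should lower. Section 5.3 expects a change in exposure in both parts, and Section 13.1.1 promises an estimate of its magnitude with a 90% confidence interval. That magnitude is what would be distorted.

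Variation in practice is plausible. About 24 centers are planned, admission on the evening of Day 14 is optional, and dosing follows standard institutional procedures. If meal state is not recorded, it may not be recoverable later.

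**Working it through.** **1. The plan's own power.** Inputs from Protocol 13.1.1 and SAP 4.2: CV 30%, correlation 0.80, n = 12, geometric mean ratio 1.06 or 0.94, 90% CI within 0.80–1.25.

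- SD on the log scale = √ln(1 + 0.30²) = 0.2936.
- SD of the log difference = 0.2936 × √(2 × (1 − 0.80)) = 0.1857.
- Exact paired two one-sided tests, 11 df, 0.05 per side: **89.1%** at 1.06 and **87.9%** at 0.94. The stated figure of 88% or higher is reproduced.

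**2. Food factors** (Protocol 5.2.2). AUC: 1 − 0.18 = 0.82, just inside 0.80–1.25. Cmax: 1 − 0.24 = 0.76, outside it. Cmax is a primary endpoint in both parts (Section 6.1).

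**3. Shift in the ratio** when a share *p* of subjects is mismatched. The AUC multiplier is 0.82^p in Part 1 and at most 0.82^(−p) in Part 2.

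| Share mismatched | 0% | 25% | 50% | 100% |
|---|---|---|---|---|
| Part 1 AUC multiplier | 1.00 | 0.95 | 0.91 | 0.82 |
| Part 2 AUC multiplier (at most) | 1.00 | 1.05 | 1.10 | 1.22 |

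At 100% the Cmax multipliers are 0.76 (Part 1) and at most 1/0.76 = 1.32 (Part 2). For scale, the planned 90% CI is the estimate multiplied or divided by exp(1.796 × 0.1857/√12) = 1.10.

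**4. Chance that the AUC interval falls within 80–125%**, n = 12. The 0% and 100% columns are exact. The 25% and 50% columns come from 400,000 simulated trials with subjects mismatched at random, so the added variance is included. SD 0.4152 is 30% CV with no credit for correlation (0.2936 × √2). SD 0.2936 assumes a correlation of 0.5.

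| True AUC ratio | SD | 0% | 25% | 50% | 100% |
|---|---|---|---|---|---|
| 1.25 (Part 1) | 0.1857 | 5.0% | 19.1% | 45.4% | 96.2% |
| 1.25 (Part 1) | 0.2936 | 5.0% | 12.5% | 25.0% | 57.3% |
| 1.25 (Part 1) | 0.4152 | 3.3% | 5.7% | 8.7% | 15.8% |
| 1.06 (Part 1) | 0.1857 | 89.1% | 94.0% | 87.0% | 42.4% |
| 1.06 (Part 1) | 0.2936 | 50.1% | 53.0% | 47.5% | 22.5% |
| 1.06 (Part 1) | 0.4152 | 14.5% | 14.4% | 13.1% | 8.7% |
| 0.94 (Part 2) | 0.1857 | 87.9% | 93.8% | 88.0% | 44.8% |

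A true 0.80 in Part 2 behaves like 1.25 in Part 1, within simulation error. The 96.2% arises because 1.25 × 0.82 = 1.025, almost no apparent effect. Power at 1.06 rises at 25% mismatch because 1.06 × 0.95 = 1.01.

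**5. Larger interactions.** With every subject mismatched, a true 1.60 meets the criterion 0.6%, 1.45% and 1.56% of the time at the three SDs; a true 0.60 does so 0.07%, 0.42% and 0.74% of the time. These interactions would be detected but mis-sized. A true 2.0 in Part 1 reads 2.00 / 1.90 / 1.81 / 1.64 across the four mismatch shares. A true 0.50 in Part 2, fully mismatched, reads up to 0.50/0.82 = 0.61.

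No Cmax pass rates are given, because the documents state no variance or correlation for Cmax.

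**The case against.** The open wording may be deliberate. The sponsor regards the food effect as negligible, sees similar exposure fed and fasted, and attaches meal rules only to the drugs it believes need them. The reported AUC ratio of 0.82 lies within 80–125%. That explains the wording but does not settle the matter: 0.82 is close to the boundary, 0.76 for Cmax is beyond it, and either shift is larger than the 6% effects the study was sized around.

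Other points do stand:

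- No mismatch is shown. The study schema figures, laboratory manual, home-dosing instructions, site procedures, eCRF and separate PK analysis plan were not available, and any of them may set or record meal state.
- The two 100% cases need opposite habits: Day 15 fasted in Part 1, fed in Part 2. One uniform practice across the study would bias at most one part.
- Part 2 figures are upper limits. No fast is stated before the Day 24 dose, and with a median tmax of 1–2 hours the meal may start at or before the peak.
- The 96% figure needs a ratio exactly on the boundary, full mismatch and the planned correlation. At SD 0.4152 it is 16%, and there variance matters more than food.
- With strong perpetrators the likelier harm is mis-sizing, not a false no-effect conclusion.

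These points limit the size of the problem. They do not remove a gap in the governing text that can bias the primary estimate.

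**Conclusion.** The concern holds and should be fixed; confidence is medium because some documents are unseen. The supplied text controls meal state in the test period and leaves it open in the reference period of the primary comparison. In Part 1 the AUC ratio could be understated by up to 18% and the Cmax ratio by up to 24%. In Part 2 the ratios could be overstated by at most 22% and 32%. Actual bias depends on the share of subjects mismatched, which the documents do not give, and is zero if subjects happen to eat on Day 15 as on the test day.

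These sizes assume that the Section 5.2.2 point values, given there without a confidence interval, apply to any meal, at 400 mg and 800 mg, equally in all subjects, and multiplicatively under inhibition or induction. Part 2 also treats one hour before a meal as unfed.

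**What to change.** In Protocol Sections 7.1 and 10.5, require the Day 15 dose to be taken after a meal in Part 1 and one hour before a meal in Part 2. For Part 2, state the same preceding fast or meal condition for Day 15 and Day 24. Record meal time on every intensive PK day.

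The documents do not name the days for the Part 1 single-dose secondary objective. If Day 1 versus Day 21 is the comparison used, match those days too. If another study document already fixes the Day 15 meal, cite it in Section 10.5.

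For subjects already studied, run a matched-meal sensitivity analysis where source records show meal state. Otherwise report the limitation, with the bounds above, beside the ratio.

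The cost is a minor restriction on mornings when subjects already attend the clinic, and one extra data field. A matched-meal subset would be smaller than 12, so it can serve only as a sensitivity analysis.

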10.5.1. Missed Doses

Tazemetostat doses must be taken 12 hours apart at approximately the same time each day, for example between 7 – 9 am for the morning dose and 7 – 9 pm for the evening dose. If a dose of any study drug (tazemetostat, itraconazole or rifampin) is missed, then that drug should be administered at the next dosing time point.

Vomiting: If the subject vomits after study drug administration, then that study drug (tazemetostat, itraconazole or rifampin) should be administered at the next dosing time point. All doses given, missed, and vomited, should be recorded.

10.6. Study Drug Accountability

The Investigator/designee will be responsible for taking an inventory of each shipment of all study drugs (tazemetostat, itraconazole and rifampin) received and comparing it with the accompanying shipment form. The Investigator/designee will verify the accuracy of the information on the form, sign, and date it, and acknowledge the shipment receipt according to the instructions provided.

The Investigator/designee must keep accurate written records of all tazemetostat, itraconazole and rifampin received from the Sponsor. Additionally, the Investigator/designee must keep accurate records of the tazemetostat, itraconazole and rifampin dispensed to subjects enrolled in this study including the quantity of tablets, lot number, date dispensed, subject initials and identification number, dose administered, balance forward, and the initials of the person dispensing the study drug. Based on the entries in the site accountability forms, it must be possible to reconcile study drugs delivered with that used and returned. All study drugs must be accounted for, and all discrepancies investigated and documented appropriately.

Tazemetostat, itraconazole and rifampin stock may not be removed from the investigative site where originally shipped without prior knowledge and consent of the Sponsor or its designee. When authorized, all applicable local, state, and national laws must be adhered to for the transfer.

10.7. Study Drug Handling and Disposal

At the end of the study, all unused tazemetostat, itraconazole and rifampin will be destroyed by the investigative site or sent to a designated contractor for disposal on behalf of the Sponsor, per the instructions at that time. Any study drugs returned to the Sponsor-designated contractors must be counted and verified by site personnel and the Sponsor or its designee. All certificates of delivery/receipts and/or return forms must be signed prior to shipment. The study drugs for return must be packed in a tamper-evident manner to ensure integrity is maintained during return. All study drugs returned must be in accordance with local, state, and national laws and must first be authorized by the Sponsor prior to shipment.

11. PHARMACOKINETIC ASSESSMENTS

11.1. Blood Sample Collection

PK blood samples will be collected at steady-state dosing intervals following multi-dose administration of tazemetostat (Table 9). All dosing and PK sampling times will be recorded. PK blood samples at post-dose timepoints that coincide with dosing of study drug(s) (ie, 12, 24, 36, 48, and 72 [Part 1 only] hour) must be collected prior to dosing of the subject at that timepoint. A laboratory manual detailing the PK sample collection, preparation, storage, and shipping process will be provided to Investigators.

Table 9: Timing Allowance Windows for Vital Sign Measurements, ECG Assessments and Pharmacokinetic Sampling

Measurement	Time Point (hours)	Timing Tolerance Window
Vital signs	0 (pre-dose)	-60 min to 0 hour
ECG	0 (pre-dose)	-60 min to 0 hour
	2	-10 min prior to 2 hours post-tazemetostat dose
	24 ^a	-60 min prior to 24 hours post-tazemetostat dose
	48 ^{a, b}	-60 min prior to 48 hours post-tazemetostat dose
PK blood sampling	0 (pre-dose)	-60 min to 0 hour
	>0 to 3	-5 min to +5 min
	4 – 12	-15 min to +15 min
	24 and >24	-60 min to +60 min

Abbreviations: ECG= electrocardiogram, PK= pharmacokinetics.

^a ECGs performed at 24 (Part 1 only) or 48 hours post-tazemetostat administration are to be performed prior to dosing of any study drugs on that day

^b No study drugs administered on Cycle 1 day 17 in Part 1 or Cycle 1 day 26 in Part 2 at 48 hours post-tazemetostat administration. Perform ECG per timing tolerance window prior to collection of 48 hour PK sample

